9.2. Study Visits – Standard of Care Treatment Period

For all visits and site contacts, assessments will be performed as indicated in the Schedule of Assessments ([Table 2](#)).

9.2.1. Screening and Enrollment

Pediatric patients who are considered good candidates for the study will report to the site for a screening visit. After the P/C have provided informed consent, and, where appropriate, children have provided assent, screening assessments may be initiated. Screening assessments will be conducted at the screening visit although, if necessary, the assessments may take place over a screening period not to exceed 14 days without prior consent of the sponsor. Subjects will be considered enrolled into the study as of the date of the screening visit if all available results satisfy the inclusion and exclusion criteria as of that date. If, after the screening visit, screening results are returned that indicate the subject no longer meets the inclusion and exclusion criteria, the subject will be considered a screen failure. The investigator will provide the P/C with study materials (eg, subject's diary) at the end of the screening visit and request the P/C to record diary data starting at the date of the screening visit and for the next 12 weeks (ie, the SOC treatment period). The P/C will be subsequently contacted via tele-contact once all screening results are available to confirm eligibility or screen failure.

Subjects will be dosed based on their weight at the Day 1 visit. Therefore, subjects who are targeted for Cohorts 1, 2, or 3 may be enrolled into the study if they are minimally below the required weight at screening as long as the investigator feels with great certainty that the subject would be at the required weight after 12 weeks in the SOC treatment period. Of note, all subjects targeted for Cohort 4 must weigh ≥ 12 kg before being enrolled into the study.

A subject with an exclusionary value may be rescreened if the investigator believes the exclusionary value obtained was not an accurate reflection of the subject's status (eg, out of range laboratory value due to compromised sample). With prior sponsor approval, subjects with an exclusionary C1-INH test result may be retested during the SOC treatment period if the results are incongruent with clinical history or considered by the investigator to be confounded by recent C1 inhibitor use.

Once enrolled, subjects will begin the SOC treatment period. During this 12-week period, subjects will continue taking their SOC therapy for HAE (either short-term or long-term prophylaxis, and/or acute treatment for HAE attacks). No additional in-person visits are required during the SOC treatment period.

9.2.1.1. Sexual Counseling

Competent adolescents should receive age-appropriate sexual counseling by a qualified health care professional to determine the adherence to inclusion criterion #7 in Section [7.2.1](#).

There are insufficient data in pregnant women available to inform drug-related risks with berotralstat use in pregnancy. If a female subject becomes pregnant during the study, study drug/IMP will be discontinued per Section [7.3.2](#) and pregnancy reporting and follow-up will be conducted as described in Section [11.1.3.2](#).

9.2.2. Weeks 4 and 8 after Enrollment

At approximately 4 ± 1 and 8 ± 1 weeks after the date of enrollment (Section 9.2.1), the site must have an interactive contact with the P/C to assess AEs and status of HAE attacks. Subjects may be included in the contact at the discretion of the investigator. Site contact may be a telephone call, telemedicine visit, or an in-person clinic visit if such a visit was otherwise planned or if the investigator believes it would be in the best interest of the subject to return to the clinic. The contact may also be an in-person consultation between site staff and the P/C if requested by either the investigator or P/C. At 8 weeks after enrollment, where possible, the subject should assess their weight at home in light clothing with shoes and other heavier items removed. The site will obtain the results of the home weight assessment by telephone and record the results in source documents.

9.3. Study Visits – Berotralstat Treatment Period: Part 1

9.3.1. Baseline Visit (Day 1)

Subjects will return to the clinic 12 weeks \pm 4 days after the date of enrollment (Section 9.2.1) for the Day 1 (baseline) visit. If extenuating circumstances would result in the baseline visit being delayed, the site must get prior approval from the medical monitor for the visit to occur outside of the defined visit window and for the subject to continue in the study. Prior to the Day 1 visit, subjects must discontinue prophylaxis for HAE as well as other specific medications.

At the baseline visit, the site will review prohibited medications (Section 8.7), subject diary entries, and discuss any AEs that occurred during the SOC treatment period. If any activities were not completed satisfactorily (eg, diary entries were incomplete or the P/C could not be contacted to assess AEs at the prescribed intervals) or the use of prohibited medications is discovered, the subject may be discontinued from the study and not enrolled into Part 1 at the sole discretion of the investigator. After final eligibility for entry into Part 1 is confirmed, subjects will receive their first dose of berotralstat in the clinic and those taking berotralstat granules for oral administration will complete the palatability/acceptability hedonic scale assessment as appropriate for the subject's age. Reference Section 8.3 for berotralstat dosing procedures. The dose of berotralstat will be determined based on the subject's weight at Day 1 and will not be adjusted during Part 1 due to weight changes. If required for medical management, any changes in berotralstat dose during Part 1 should be discussed with the BioCryst medical monitor prior to implementation. Details can be found in Section 8.4.

9.3.2. Weeks 2, 6, 9, and 12

All subjects will return to the clinic for visits during Weeks 2, 6, and 12 following baseline and the site will contact the P/C (tele-contact) during Week 9.

At the Week 2 visit, a series of blood samples will be collected for PK analysis (Section 10.9). To ensure the trough sample provides accurate PK information, the Week 2 visit should be scheduled as close as possible to the regularly scheduled time of dosing for the subject. The dose of berotralstat should be given in the clinic with food (a snack or light meal should be provided). A blood sample for PK analysis will be collected before dosing and at the times post dosing as shown in the Schedule of Assessments.

At the Week 12 visit, the subject will move from Part 1 into Part 2. The subject will be weighed and the dose of berotralstat will be adjusted according to the current weight of the subject (Table 1).

9.4. Study Visits – Berotralstat Treatment Period: Part 2

9.4.1. Week 16, 20, 28, 32, 40, and 44 Contacts

The investigator (or designee) must contact the P/C at the weeks shown in the Schedule of Assessments via an interactive method, eg, telephone discussion or telemedicine visit. During the contact, the investigator (or designee) will assess the subject's overall wellbeing, collect information on any AEs that may have been experienced by the subject, discuss compliance, and proper recording of attack details (if applicable). If warranted for medical management of the subject or if requested, the contact may be an in-person visit. In this case, visit information should be recorded in the CRF according to directions provided in the CRF completion instructions.

9.4.2. Week 24, 36, and 48 Visits

All subjects will return to the clinic during study Weeks 24, 36, and 48 for appropriate assessments.

A plasma sample for PK analysis will be collected at these visits. The date and time of the preceding dose of berotralstat must be captured and recorded in the source documents and CRF.

9.5. Study Visits – Berotralstat Treatment Period: Part 3

9.5.1. Week 60, 84, 108, and 132 Contacts

The investigator (or designee) must contact the P/C at the weeks shown in the Schedule of Assessments via an interactive method, eg, telephone discussion or telemedicine visit. During the contact, the investigator (or designee) will assess the subject's overall wellbeing, collect information on any AEs that may have been experienced by the subject, concomitant medications taken by the subject, and discuss compliance (if applicable). If warranted for medical management of the subject or if requested, the contact may be an in-person visit. In this case, visit information should be recorded in the CRF according to directions provided in the CRF completion instructions.

9.5.2. Week 72, 96, and 120 Visits

Following the Week 48 visit, subjects should return to the clinic every 24 ± 1 weeks for clinic visits.

9.5.3. Week 144 / End of Treatment (EOT)

Subjects will return to the clinic for the EOT visit at Week 144 (± 1 week). Any subject who discontinues the study during Part 3 should return to the site as soon as possible to complete the Week 144 (EOT) assessments.

If an AE is ongoing at the last study visit, additional clinic visit(s) or telephone contact(s) may be warranted (see Section 11.1.1.4).

9.6. End-of-Study (EOS) Follow-up Visit

Subjects who discontinue berotralstat either at the Week 144 visit or earlier will be required to attend a follow-up visit 3 weeks (21 ± 3 days) after study drug discontinuation. Subjects will be discontinued from the study at this visit. Subjects who discontinue the study but will continue to receive berotralstat via another mechanism will have end-of-study assessments performed at their last regularly scheduled visit. After Week 48, subjects who discontinue study drug but continue to receive berotralstat via another mechanism will be considered completers.

If an AE is ongoing at the EOS visit, additional clinic visit(s) or telephone contact(s) may be warranted (see Section 11.1.2.1).

10. ASSESSMENTS

The schedule of procedures and assessments to be conducted throughout the study are outlined in the Schedule of Assessments (Table 2).

To the extent possible, the following chronology of events should be adhered to during the scheduled visits:

- ECGs: obtain prior to vital signs and blood specimen collection
- Vital signs: obtain prior to blood specimen collection
- Study drug dispensing/dosing: end of the visit

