4.4.5. Berotralstat Risk Analysis

Potential risks and findings from nonclinical and clinical studies of berotralstat are discussed in Section 6 of the IB (Summary of Data and Guidance for the Investigators). Adverse reactions seen during clinical trials with berotralstat at 150 mg once daily (QD) include abdominal pain, vomiting, diarrhea, and gastroesophageal reflux disease. In the prescribing information, a warning and precaution is noted for an increase in QT prolongation which can occur at dosages higher than the recommended adolescent and adult dose of 150 mg QD.

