- ^l For all girls of childbearing potential, a serum pregnancy test will be administered at screening. Urine pregnancy tests will be assessed at all subsequent visits as indicated in the table. A serum pregnancy test should immediately be drawn and sent for analysis for any positive urine pregnancy test. In addition, girls of childbearing potential will be dispensed urine pregnancy tests to complete at home approximately every 4 weeks, where dictated by local requirements; participants will receive the appropriate number of pregnancy tests to complete testing at the intervals above during in-person clinic visits as needed. Sites will obtain the home test results during planned site contacts and record the results in source documents.
- ^m To qualify for entry into Part 1, subjects must discontinue use of listed medications at the times indicated. Note that the times are relative to the Day 1/baseline visit. Refer to exclusion criteria ([Section 7.2.2](#)) for further explanation.
- ⁿ Subjects should have alanine aminotransferase (ALT), aspartate aminotransferase (AST), alkaline phosphatase (ALP), lactate dehydrogenase (LDH), gamma-glutamyl-transpeptidase (GGT), and total and direct bilirubin measured 2 weeks (+ 7 days) after androgen discontinuation.
- ^o The final dose of SOC prophylaxis must be administered no later than the day before the Day 1/baseline visit. Subjects may continue to take medication to treat acute attacks throughout the study.
- ^p All ECGs during the study will be single assessments with the exception of baseline, which will be obtained in triplicate. An ECG should be repeated for a change from baseline in QTc > 60 msec or a QTc interval > 500 msec. Prior to obtaining an ECG, subjects should rest quietly. When possible, ECGs should be obtained prior to any blood sampling.
- ^q If adverse events commonly associated with prolonged QTc interval (eg, unexplained intermittent or continuous lightheadedness, syncope, palpitation, chest pain) are reported or the dose is modified, additional ECGs should be recorded.
- ^r The site should contact the P/C by the method agreed upon at the screening visit; the contact may be by telephone or may be a telemedicine visit.

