10.4. Weight/Height/Body Mass Index

Subject weight is important for this study as the dose of berotralstat will be based on subject weight. Therefore, the site should be diligent in accurately taking and recording subject weight. Subjects should be weighed in light clothing with shoes and other heavier items (eg, belts or phones) removed. Heavier outer clothing (eg, jackets or sweaters) should also be removed.

Height should be recorded at the indicated visits. Body mass index (BMI) should be calculated at all visits where weight and height are measured using the following formula:

$$\text{BMI} = \text{weight (kg)} / \text{height (m)}^2$$

10.5. 12-lead Electrocardiograms

A standard bedside or routine 12-lead ECG machine that calculates heart rate and measures the PR, QRS, QT, RR, and QTc intervals will be used. Prior to obtaining an ECG, subjects should rest quietly for at least 10 minutes. Resting may be in a supine position or other position (eg, on the P/C's lap) as age appropriate for the subject.

Qualified site personnel should review the ECGs and automated findings in real time for gross abnormalities and interval measurements of concern (absolute readings and for post-baseline ECGs, a change from baseline). For all ECGs, the clinical interpretation of the ECG and calculated QTc should be recorded directly on a hard copy of the ECGs. Copies of the ECGs may be requested by the sponsor. All subject identifiers will be masked prior to provision to the sponsor.

Baseline (pre-dose) ECGs will be obtained in triplicate (ie, 3 separate readings taken at 1- to 5-minute intervals) with baseline values calculated from an average of the 3 readings. All other ECGs will be single assessments.

An ECG should be repeated for a change from baseline in QTc > 60 msec or a QTc interval > 500 msec.

If AEs commonly associated with prolonged QTc interval (eg, unexplained intermittent or continuous lightheadedness, syncope, palpitation, chest pain) are reported or the dose is modified, additional ECGs should be recorded. ECGs obtained due to dose modification should be taken approximately 2 to 6 weeks after dose modification and should be aligned with PK blood sample timelines described in Section 10.9.1 to the extent possible.

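### If the stated visit order is followed, the only Week 2 ECG is taken before the dose, at about trough, and no ECG in the main schedule is timed to a post-dose window

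*Protocol*

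**What the plan says.** Protocol section 10 introduces a visit order with "To the extent possible, the following chronology of events should be adhered to during the scheduled visits". It lists "ECGs: obtain prior to vital signs and blood specimen collection" first and "Study drug dispensing/dosing: end of the visit" last. Table 2 footnote p agrees: "When possible, ECGs should be obtained prior to any blood sampling". The SAP reproduces that footnote under its own Table 2. Section 10.5 makes the Day 1 ECG a pre-dose triplicate and every later ECG a single reading.

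For Week 2, section 9.3.2 says "A blood sample for PK analysis will be collected before dosing and at the times post dosing as shown in the Schedule of Assessments". Section 10.9 sets the post-dose times at 1, 2, 4 and 6 hours in Cohorts 1 to 3, and at 1 to 2 and 4 to 6 hours in Cohort 4. After Week 2, section 8.3.2 moves dosing to the child's largest meal and does not require it to be shifted for clinic visits.

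Section 4.4.5 notes a labelled warning about an "increase in QT prolongation which can occur at dosages higher than the recommended adolescent and adult dose of 150 mg QD". Section 7.3.2 gives two QTcF discontinuation criteria. Each lets the dose be interrupted or reduced first if there is an associated Cmax above the adult range, and sections 11.2.1 and 11.2.2 repeat the link. The one ECG tied to PK timing is the extra ECG after a dose modification, which "should be aligned with PK blood sample timelines described in Section 10.9.1 to the extent possible".

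**The concern.** The protocol treats QT risk as a matter of exposure, and its QTcF rules refer to peak concentration. Week 2 is the only scheduled visit that samples across the hours after a dose, and its Cmax can lead to a dose change (Table 2 footnote x). If the ECG comes before the first draw that day, its QTcF is matched in time to the pre-dose concentration and to none of the post-dose concentrations.

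SAP section 11.5 summarises QTcF values, categories and changes from baseline by time point and cohort. It plans nothing by time since dose or by concentration. The Week 2 rows would therefore describe the effect at about trough, and the later rows would mix unknown times since dose. A reader of those tables could take a clean Week 2 result as evidence about peak exposure, which it would not be.

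**Working it through.** This is a question of timing, and the plan states no figure to reproduce. The check sets the provisions side by side.

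**1. Scheduled ECGs and PK samples** (Table 2; sections 8.3.2, 9.3.2, 10.5, 10.9)

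| Visit | ECG | Scheduled PK | ECG time relative to dose |
|---|---|---|---|
| Day 1 | Triplicate | None | Pre-dose |
| Week 2 | Single | Pre-dose, then post-dose series | Before the pre-dose draw, if the order is followed |
| Week 6 | Single | None (a missed Week 2 series may be taken by this visit) | Not set |
| Weeks 12, 24, 36, 48 | Single | One random sample, last dose time recorded | Not set |
| Week 144 | Single | None | Not set |
| End of study | Single | None | 3 weeks after the last dose, where the drug is stopped |

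On-treatment ECGs: 1 + 1 + 4 + 1 = 7. One is pre-dose by sequence, six are untimed, and none is timed to a post-dose window.

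**2. Week 2 in order.** The sequence is ECG, vital signs, pre-dose draw, dose, post-dose draws. In Cohorts 1 to 3 the post-dose windows run from 1 − 0.5 = 0.5 hours to 6 + 1 = 7 hours. The ECG precedes all of them. Section 9.3.2 asks for the visit to be close to the child's usual dosing time, so the ECG falls near the end of the previous dosing interval.

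**3. An internal conflict.** Dosing at the end of the visit (section 10) cannot hold at Week 2, because the post-dose series must follow the dose. The general list was not adapted to this visit.

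**4. Could an untimed ECG still fall near peak?** Assume, for illustration only, that each of the six untimed ECGs falls independently and uniformly over the 24 hours after a dose.
- 2 to 4 hours after dose: 2/24 = 8.3% for one ECG; at least one of six, 1 − (1 − 2/24)^6 = 41%.
- 1 to 6 hours after dose: 5/24 = 20.8% for one ECG; at least one of six, 1 − (1 − 5/24)^6 = 75%.

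So *none is timed near peak* is right, and *none will fall near peak* would be wrong.

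**5. Size of a missed effect.** If the QT effect were proportional to concentration, a trough reading would miss a share 1 − 1/r of the peak effect, where r is the peak-to-trough ratio. The documents give no r. Assumed values of 1.1 and 3 give 1 − 1/1.1 = 9% and 1 − 1/3 = 67%. That range is too wide to support a figure.

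**6. The dose-modification ECG.** Section 10.9.1 has a 20 to 24 hour sample and a 2 to 4 hour post-dose sample, the second only if possible in Cohorts 3 and 4. Section 10.5 does not say which of the two the ECG should be aligned with.

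**The case against.** The strongest reply is that the order is best effort. Section 10 and footnote p are both qualified, the end-of-visit dosing item already has to give way at Week 2, and nothing forbids a later ECG. That stands, and it limits the point to sites that follow the stated order. But nothing directs a site to a post-dose ECG either.

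The plan also has other safeguards. At Weeks 12, 24, 36 and 48 an ECG and a PK sample are taken at the same visit with the last dose time recorded, so QTcF could be related to concentration there. Week 2 Cmax is itself checked and can change the dose. Symptoms associated with QT prolongation prompt extra ECGs, and SAP section 11.1 adds a torsade/QT table. Doses were chosen to match adult Cmax and Ctrough (section 4.4.2), and the label warning concerns dosages above 150 mg. All of this stands and lowers the stakes. It does not fill the Week 2 gap, and the SAP plans no QTcF-concentration analysis of the later visits.

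A reader might infer two stronger things. One is that ECGs from Week 6 on tend to fall late in the dosing interval. Section 8.3.2 does not support this: it names no particular meal, and a child dosed before the visit would have an early post-dose ECG. The other is that a rise above 60 msec at peak would go unseen. The documents give neither the ratio nor the concentration-QT slope needed to say so.

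**Conclusion.** The point holds as a cheap improvement, not as a demonstrated failure of QT monitoring. When the stated order is followed, every child's single Week 2 QTcF is read before the dose, at about trough. No ECG in the main schedule (0 of 7 on treatment) is timed to a post-dose window. Time since dose at Weeks 6, 12, 24, 36, 48 and 144 is uncontrolled, so a near-peak reading occurs only by chance. The Week 2 QTcF therefore cannot be read beside a same-day post-dose concentration taken at the same time, at the one visit designed to characterise Cmax.

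This rests on sites following a best-effort order and on the Week 2 series being collected at Week 2. The clinical size of any missed effect is unknown from these documents.

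**What to change.** Add a Week 2 exception to section 10 and to Table 2 footnote p, with the same edit to the SAP's copy of that footnote. The existing single ECG would be taken after the in-clinic dose, immediately before one of the post-dose PK draws already scheduled. The sponsor should choose the draw from the Tmax in its own PK model. Time from dose should be recorded and the 10-minute rest in section 10.5 kept.

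Reconcile the end-of-visit dosing item in section 10 with the Week 2 series in 9.3.2 and 10.9. In 10.5, state that the post-modification ECG is aligned with the post-dose sample of 10.9.1 where that sample is taken.

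The cost is a few sentences in an amendment. No visit, ECG or blood draw is added, and doses and QTcF limits are unchanged. There is a small scientific cost: the reading follows food and an earlier draw, is less closely time-matched to the pre-dose Day 1 baseline, and replaces the Week 2 trough reading.

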10.1. Demographics

Demographic information, including month and year of birth, sex, race, and ethnicity (as applicable or as permissible by country requirements) will be captured for each subject participating in the study at the screening visit. Medical and medication history will be captured at the screening visit and updated at enrollment (if different from the screening visit).

